Mean daily dose of Nesina	
Calculate using the following formula: Total of “daily dose of Nesina \square Nesina treatment period at the relevant dose” / Nesina treatment period. For the calculation of Nesina treatment period, refer to the above.
 
If the daily dose of Nesina is a number outside specification in the survey sheet , handle the dose as follows:
 
 • < 6.25 mg \rightarrow 3.125 mg • > 25 mg \rightarrow 50 mg
HbA1c (NGSP value)	
The NGSP value only will be used in this analysis.
 
For the HbA1c (JDS value), calculate using the following formula: NGSP value (%) = $1.02 \times \text{JDS value (\%)} + 0.25\%$
 
The HbA1c (international standard value) will be handled as the NGSP value.

Change in HbA1c	For HbA1c converted to the NGSP value, calculate using the following formula: Laboratory value at each testing time point – Laboratory value at the start of Nesina treatment.
Glycemic control achievement rate	
Divide the following two categories for the glycemic control achievement rate: HbA1c (NGSP converted value) [Unit %] NGSP (%): < 6.0, \geq 6.0 / < 7.0, \geq 7.0

non-HDL cholesterol	Calculate using the following formula: “Total cholesterol” – “HDL cholesterol.”
HOMA-R	Calculate using the following formula: Fasting insulin level ($\mu\text{U/mL}$) \times Fasting blood glucose level (mg/dL) / 405. Indicate to one decimal place rounded from two decimals. For calculation, use the values of fasting insulin level and fasting blood glucose level measured at the same day.
HOMA- β	
Calculate using the following formula: Fasting insulin level ($\mu\text{U/mL}$) \times 360 / (Fasting blood glucose level [mg/dL] – 63). Indicate to one decimal place rounded from two decimals.
 
For calculation, use the fasting insulin level and fasting blood glucose level measured at the same day. Do not use the fasting blood glucose level of < 63 for calculation

Summary statistics	Number of patients, mean, standard deviation, minimum, first quartile, median, third quartile, and maximum.

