### 8.0 Scheduled Period

Survey period: June 2014 to June 30, 2017

Patient enrollment period: June 2014 to June 30, 2016\*

\*Even if Nesina is prescribed before June 30 2016, the patients cannot be enrolled (fax of the Patient Enrollment Sheet) after July 1 2016.

In case that the enrolled participants reach the scheduled number of participants in the survey before June 30 2016, the enrollment will close earlier than the scheduled patient enrollment period. If patient enrollment period is shorten, the survey period will be also changed according to the shorten period.

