##### 9.2.2 Patient Demographics

###### 1) Matters to be surveyed

Diagnosis period of type 2 diabetes mellitus, category of clinical practice, disposition of hypersensitivity (yes/no and detail), concurrent disease (yes/no and detail), past medical

history (yes/no and detail), height, smoking history, drinking history, presence or absence of serum creatinine within 1 month after the start of Nesina treatment, serum creatinine level (if serum creatinine present), and severity of renal impairment and rationale for the assessment (if serum creatinine absent).

2) Survey period

At the start of Nesina treatment

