Age	If the start month and date of Nesina treatment is earlier than the birth month and date, calculate using the following formula: Start year of Nesina treatment – birth year – 1. If the birth month and date is earlier than or equal to the start month and date of Nesina treatment, calculate using the following formula: Start year of Nesina treatment – birth year. For unknown birth date, the birth date will be calculated as the 1st day of the birth month.
BMI	Calculate using the following formula: Weight (kg) / (0.0001 \times Height (cm) \times Height (cm)). Indicate to one decimal place rounded from two decimals.
Disease duration of type 2 diabetes mellitus (year)	Calculate using the following formula: (start date of Nesina treatment – diagnosis period of type 2 diabetes mellitus + 1) / 365.25. For unknown diagnosis month, calculate as January. Indicate to one decimal place rounded from two decimals.
Prior medication	Medications that patients were taking within 3 months prior to the start of Nesina treatment.
Concomitant medication	Medications that patients were taking after the start date of Nesina treatment.
Start date of other diabetic drug and concomitant medication (other than diabetic drug)	Calculate as the start date of survey sheet. For unknown month and date, calculate as January 1. For unknown date only, calculate as the first day of the relevant month.
End date of other diabetic drug and concomitant medication (other than diabetic drug)	Calculate as the end date of survey sheet. For unknown month and date, calculate as December 31. For unknown date only, calculate as the last day of the relevant month.
Diabetic drugs	Drugs of the National Health Insurance (NHI) Drug List Code starting with 3969, 3961, 3962, 2492, 2499410, 2499411, 2499415, or 2499416.
α -glucosidase inhibitors	Drugs of the NHI Drug List Code starting with 3969003, 3969004, 3969009, or

Term	Definition
	3969102.
Thiazolidines	Drugs of the NHI Drug List Code starting with 3969005, 3969007, 3969100, 3969101, or 3969103.
Sulfonylureas	Drugs of the NHI Drug List Code starting with 3961 or 3969101.
Biguanides	Drugs of the NHI Drug List Code starting with 3962, 3969100, 3969104, or 3969105.
Rapid-acting insulin secretagogues	Drugs of the NHI Drug List Code starting with 3969006, 3969008, 3969013, or 3969102.
Insulin preparations	Drugs of the NHI Drug List Code starting with 2492.

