1.6 Display Data Digit

Display digits are described as below.

Term	Display digit	Unit
HbA1c (NGSP value)	0.1	%
Fasting blood glucose level	1	mg/dL
Fasting insulin level	0.1	μU/mL
Fasting glucagon	0.1	pg/mL
HOMA-R	0.1	—
HOMA-β	0.1	%
Fasting triglyceride	1	mg/dL
Total cholesterol	1	mg/dL
HDL-cholesterol	1	mg/dL
LDL-cholesterol	1	mg/dL
non-HDL cholesterol	1	mg/dL
Serum creatinine	0.01	mg/dL
BUN	0.1	mg/dL
Urinary albumin (corrected by creatinine)	0.1	mg/g•Cre
AST	1	IU/L
ALT	1	IU/L
γ-GTP	1	IU/L
ALP	1	IU/L
Total bilirubin	0.1	mg/dL
Amylase	1	IU/L

Term	Display digit	Unit
Lipase	1	IU/L
Waist circumference	0.1	cm
Pulse rate	1	bpm
Systolic blood pressure	1	mmHg
Diastolic blood pressure	1	mmHg
Weight	0.1	kg
BMI	0.1	kg/m ²
Age	1	Year
Duration of type 2 diabetes mellitus	0.1	Year
Height	1	cm
eGFR	0.1	mL/min/1.73 m ²
Nesina administration period	1	Day
Mean daily dose of Nesina	0.01	mg

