3.0 Patient Demographics

(1) Patients to be tabulated and analyzed

Safety Analysis Set

(2) Details of tabulation and analysis

Each parameter will be classified by the categories described below to tabulate the number of patients and frequency.

Total patients and patients who are taking concomitant insulin preparation, rapid-acting insulin secretagogues, SGLT-2 inhibitors, or other drugs will be tabulated.

Parameter	Category
Sex	Male, Female
Age	Summary statistics
	< 65 years, ≥ 65 years
	< 75 years, ≥ 75 years
	< 20 years, 20 to 29 years, 30 to 39 years, 40 to 49 years, 50 to 59 years, 60 to 69 years, 70 to 79 years, ≥ 80 years
Disease duration of type 2 diabetes mellitus (year)	Summary statistics
	< 2 years, 2 to < 5 years, 5 to < 10 years, ≥ 10 years, Unknown
Height	Summary statistics
Category of clinical practice	Outpatient, Inpatient
Pregnancy (only females)	No, Yes
Severity of renal impairment	Normal, Mild, Moderate, Severe
	Normal + Mild, Moderate + Severe
Concurrent disease	No, Yes
Diabetic complication	No, Yes
Details of diabetic complication (overlapped)	Diabetic nephropathy, diabetic retinopathy, diabetic neuropathy For the proportion, the number of patients with diabetic complication will be denominator.
Concurrent hypertension	No, Yes
Concurrent dyslipidemia	No, Yes
Concurrent hyperuricemia	No, Yes
Concurrent liver disorder	No, Yes

Parameter	Category
Details of concurrent liver disorder (overlapped)	Hepatic steatosis, alcoholic hepatitis, chronic hepatitis, hepatic cirrhosis, or other For the proportion, the number of with concurrent liver disorder will be denominator.
Severity of hepatic impairment	Normal, Grades 1, 2, and 3, or Unknown
Concurrent renal disorder	No, Yes
Details of concurrent renal disorder (overlapped)	Nephrotic syndrome, glomerulonephritis, chronic glomerulonephritis, other For the proportion, the number of with concurrent renal disorder will be denominator.
Severity of renal impairment (eGFR)	Normal, Mild, Moderate, Severe, or Unknown
	Normal + Mild, Moderate + Severe, or Unknown
Severity of renal impairment (serum creatinine)	Normal, Mild, Moderate, Severe, or Unknown
	Normal + Mild, Moderate + Severe, or Unknown
Concurrent heart disease	No, Yes
Details of concurrent heart disease (overlapped)	Cardiac failure, myocardial infarction, angina pectoris, other For the proportion, the number of with concurrent heart disease will be denominator.
Concurrent cardiac failure	No, Yes

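### For patients whose diagnosis month is unknown, the SAP's January rule can only lengthen diabetes duration, by about half a year on average; the effect is confined to the descriptive demographics table

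*SAP*

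**What the plan says.** SAP 1.1 derives duration in years by a formula that ends "start date of Nesina treatment – diagnosis period of type 2 diabetes mellitus + 1) / 365.25", and adds the rule "For unknown diagnosis month, calculate as January". No day within January is given. The rule is the same in all three SAP versions in the file.

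The result is displayed to one decimal place (SAP 1.6: "Duration of type 2 diabetes mellitus 0.1 Year"). SAP 3.0 reports it in Table 3.0-1 as summary statistics and in the classes "< 2 years, 2 to < 5 years, 5 to < 10 years, ≥ 10 years, Unknown", for the total and for each treatment-group column. The rule gives a patient with a known year but no month a numerical duration, so that patient is placed in one of the four numerical classes.

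The input is a survey-sheet item collected at the start of treatment (Protocol 9.2.2: "Diagnosis period of type 2 diabetes mellitus, category of clinical practice"). Protocol 10.2 names disease period among the demographics to be tabulated. Neither document says how often the month is missing, and the SAP plans no count or flag of imputed months.

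**The concern.** Setting a missing month to the earliest possible one pushes every error the same way. Enrolling more patients does not average it out. Patients can cross the 2-, 5- and 10-year cuts upward only, and the typical error is several times the 0.1-year display precision.

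What is at stake is description. Table 3.0-1 tells the reader how long-standing the diabetes was in the surveyed population. A rule that only lengthens duration makes that population look slightly further into its disease than it was.

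**Working it through.** The plan states no figure on this point, so there is none to reproduce. The check applies the SAP formula directly.

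**Inputs from the documents**
- Formula and January rule: SAP 1.1.
- Classes: SAP 3.0. Display to 0.1 year: SAP 1.6.
- Range of treatment starts for the simulation: Protocol 8.0, "Patient enrollment period: June 2014 to June 30, 2016".

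**Assumptions not in the documents**
- True diagnosis dates are spread evenly over the calendar year.
- January is read as 1 January.
- The share *f* of patients with an unknown month is shown as a range.

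**One patient.** Nesina starts on 1 March 2015 and the true diagnosis is October 2013, with only the year recorded.
- From 1 October 2013: (92 + 365 + 59 + 1)/365.25 = 517/365.25 = 1.4 years, class < 2.
- January rule: (365 + 365 + 59 + 1)/365.25 = 790/365.25 = 2.2 years, class 2 to < 5.
- July instead: (184 + 365 + 59 + 1)/365.25 = 609/365.25 = 1.7 years, class < 2.

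**Mean overstatement per unknown-month patient**
- Against month-level duration the error is 0, 1, …, 11 months with equal weight. The mean is 5.5 months, and 5.5/12 = 0.46 year (maximum 0.91 year counted in days).
- Against the true day the error is 0 to 364 days. The mean is 182/365.25 = 0.50 year (maximum 1.00).
- A simulation of 400,000 patients, with starts uniform over June 2014 to June 2016, gave 0.46 and 0.50 under each of three assumed duration distributions: uniform 0–20 years, uniform 0–30 years, and exponential with mean 10 years. For the few diagnosed in the calendar year of the start it was smaller, about 0.29 year at month level.

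**Movement between classes**
- The largest month-level error is 11 months, so only true durations from 2 − 11/12 = 1.08 up to 2 years can leave the shortest class. About half of that band does. With durations even over 0–2 years this is (0.92/2) × 0.5 = 23%.
- Simulated, for unknown-month patients by true class:

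| True class | Moved up, January | Moved down, January |
|---|---|---|
| < 2 years | 22–24% | 0% |
| 2 to < 5 years | 14–16% | 0% |
| 5 to < 10 years | 7–9% | 0% |

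If the value is rounded to 0.1 year before classing, the first row becomes 24–26% moved up.

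**Effect on the whole table.** The shift in the overall mean is *f* × 0.46 (month level) or *f* × 0.50 (true day).

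| *f* | × 0.46 | × 0.50 |
|---|---|---|
| 10% | 0.05 | 0.05 |
| 30% | 0.14 | 0.15 |
| 100% | 0.46 | 0.50 |

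The fall in the < 2-year share also depends on the true distribution. Under an assumed gamma with mean 8 and SD 7 years, it goes from 16.5% to 11.8% at *f* = 100%. With mean 12 and SD 8, it goes from 3.3% to 1.9%. The fall is proportional to *f*, so at 10% it is 0.1 × 4.7 = 0.47 and 0.1 × 1.4 = 0.14 percentage points. That is about 5 and about 1 of the 1,000 planned patients.

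**Alternative rule**
- July is month index 6 against a mean of 5.5, so the month-level bias is −0.5/12 = −0.04 year. The simulation, with July capped at the start date, also gives −0.04.
- About 5% of unknown-month patients truly < 2 years then move up, and 5–6% of those truly 2 to < 5 years move down.
- With the same-year midpoint added, under the two gamma models and against the true day, the means return to their true values and every class share to within about 0.1 percentage point. Against month-level duration the class shares can differ by up to 0.5 point at *f* = 100%.

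**The case against.** The strongest reply is that nothing in the results depends on this. Duration is not among the factors for adverse drug reactions (SAP 5.4.1), the later breakdowns (SAP 5.5 to 5.18) or the HbA1c factors (SAP 6.4), and no test compares it between columns. That stands, and it keeps the point minor.

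The second reply is that the unknown-month share is not in the documents. At 10% the effect is 0.05 year and a handful of patients. That also stands: the size in the table cannot be stated, only its direction and its size per affected patient.

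The third reply is consistency. SAP 1.1 also uses earliest dates for adverse-event onset with unknown month, for drug starts and for the day of birth. This is weaker. For drugs, the earliest start is paired with the latest end, which widens the exposure window and can be defended as capturing any overlap. Duration has no such purpose to serve. Pre-specification makes the rule reproducible but does not remove its bias.

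Three stronger readings are tempting, and the documents do not support them:
- A reader might infer that duration in the surveyed population is half a year too long. The half year applies only to patients with an unknown month.
- A reader might infer that the shortest class is largely emptied. Only unknown-month patients with a true duration of about 1.1 to 2 years can leave it.
- A reader might infer that the bias differs between the insulin, secretagogue and SGLT-2 columns. Nothing in the documents shows the month missing more often in one group than in another.

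**Conclusion.** The point holds for patients with an unknown diagnosis month. The direction of the error follows from the rule alone. The mean of 0.46 year (month level) or 0.50 year (true day, January read as 1 January) needs the even-spread assumption, but did not vary across the duration distributions tried. The effect on the table as a whole scales with a share that the documents do not give. The rule is stated clearly and contradicts nothing else in the plan; it is a one-sided convention where a nearly unbiased one is equally simple. Label: free improvement, minor.

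**What to change.** In SAP 1.1, replace the January rule with: *If the diagnosis month is unknown, use July of the diagnosis year, with the same day convention as for known months; if that is also the year in which Nesina was started, use the midpoint between 1 January and the Nesina start date.* The second clause prevents negative durations. Add one row to Table 3.0-1 with the number of imputed months per column, so that readers can judge how much the imputation matters.

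Individual patients can still land in the wrong class, but in both directions, so the errors roughly cancel. The cost is one sentence, one derivation line and one count row, with no new data. Mean duration would come out slightly shorter than under the present rule, and this variable would depart from the earliest-date convention used elsewhere in SAP 1.1.

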	
If the onset month and date of an adverse event (or adverse drug reaction, etc.) is unknown, calculate the onset month and date as January 1. However, if the start month and date of Nesina treatment are same as the onset month and date of an adverse event (or adverse drug reaction, etc.), the onset period will be calculated as the start date of Nesina treatment.
 
For unknown onset date of adverse events (or adverse drug reactions, etc.), the onset period will be calculated as 1 day. However, if the start month and date of Nesina treatment are same as the onset month and date of adverse events (or adverse drug reactions, etc.), the onset period will be calculated as the start date of Nesina treatment.

Treatment group	
Overall: Total patients who will be treated with combination therapy with insulin preparation, rapid-acting insulin secretagogues, SGLT-2 inhibitors, and other (all are defined below)
 
Combination with insulin preparation: Patients who will be treated with insulin preparation within 3 months prior to Nesina treatment and during Nesina treatment (including at the start of Nesina treatment) and not treated with rapid-acting insulin secretagogues or SGLT-2 inhibitors
 
Combination with rapid-acting insulin secretagogues: Patients who will be treated with rapid-acting insulin secretagogues within 3 months prior to Nesina treatment and during Nesina treatment (including at the start of Nesina treatment) and not treated with insulin preparation or SGLT-2 inhibitors
 
Combination with SGLT-2 inhibitors: Patients who will be treated with SGLT-2 inhibitors within 3 months prior to Nesina treatment and during Nesina treatment (including at the start of Nesina treatment) and not treated with insulin preparation or rapid-acting insulin secretagogues
 
Other: Patients who will not be treated with combination therapy with insulin preparation, rapid-acting insulin secretagogues, or SGLT-2 inhibitors

Patients with diabetic complication	Patients with any of the following complications: diabetic nephropathy, diabetic retinopathy, or diabetic neuropathy.
Patients with diabetic nephropathy	Patients with complication of PT Code 10012660 (diabetic end stage renal disease) or 10061835 (diabetic nephropathy).
Patients with diabetic retinopathy	Patients with complication of PT Code 10012688 (diabetic retinal oedema) or 10012689 (diabetic retinopathy).

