2.0 Disposition of Patients (Patient Diagram)

(1) Patients to be tabulated and analyzed

Registered patients

(2) Details of tabulation and analysis

The following will be tabulated: the number of registered patients, number of medical site at which patients is registered, number of patients whose survey sheets are collected, number of patients whose survey sheets are not collected, number of patients in the Safety Analysis Set, number of patients in the Not Safety Analysis Set, number of patients in the Efficacy Analysis Set, and number of patients in the Not Efficacy Analysis Set.

For the number of medical sites at which patients are registered, do not duplicate the same medical site with different departments.

For patients whose survey sheets are not collected, tabulate the number of patients for each reason for not collected survey sheets.

For the Not Safety Analysis Set and Not Efficacy Analysis Set, the number of patients will be tabulated for each reason for exclusion to create the list.

The following is the handling of the decision whether patients who meet the following criteria should be evaluated:

Criterion	Safety evaluation	Efficacy evaluation
Pre-agreement administration [found after administration]	×	×
Registration 15 days after prescription of Nesina [found after registration]	×	×
Nesina taking not confirmed [after the end of patient registration period]	×	×
No data for post-administration of Nesina	×	×
Not using any of the 3 combination drugs (the treatment group will be classified as "Other.") (1) With insulin preparation (2) With rapid-acting insulin secretagogues (3) With SGLT-2 inhibitors	○	×

○ Included, × Excluded or not evaluated

(3) Number of tables and figures

Figure 2.0-1 and Table 2.0-1

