6.2 Glycemic control achievement rate (HbA1c)

(1) Patients to be tabulated and analyzed

Efficacy Analysis Set

(2) Details of tabulation and analysis

The glycemic control achievement rate for HbA1c (NGSP value) will be tabulated ($< 6.0\%$, $\geq 6.0\%$ / $< 7.0\%$, $\geq 7.0\%$) and a bar graph will be created at each testing time point (start of Nesina treatment, 1 month, 3 months, 6 months, and 12 months after Nesina treatment and last evaluation) (the unknown category will be excluded for the bar graph).

Total patients and patients who are taking concomitant insulin preparation, rapid-acting insulin secretagogues, SGLT-2 inhibitors, or other drugs will be tabulated.

(3) Number of tables and figures

Table 6.2-1 and Figures 6.2-1 and 6.2-2

6.3 Changes in Fasting blood glucose level, Fasting insulin level, Fasting Glucagon, HOMA-R, and HOMA- β

(1) Patients to be tabulated and analyzed

Efficacy Analysis Set

(2) Details of tabulation and analysis

For fasting blood glucose level, fasting insulin level, fasting glucagon, HOMA-R, and HOMA- β , summary statistics will be calculated at each testing time point (start of Nesina treatment, 1 month, 3 months, 6 months, and 12 months after Nesina treatment and last evaluation). For changes, summary statistics and the mean 95% confidence intervals will be

calculated and the paired t-test will be performed.

Measured values will be plotted and for the changes a bar graph will be created excluding the unknown category.

Total patients and patients who are taking concomitant insulin preparation, rapid-acting insulin secretagogues, SGLT-2 inhibitors, or other drugs will be tabulated.

(3) Number of tables and figures

Tables 6.3-1 and 6.3-5 and Figures 6.3-1 and 6.3-5

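### Minor: the HOMA-β rule excludes fasting glucose only below 63 mg/dL, so a reading of 63 divides by zero, and the paired t-test on HOMA-β change is fragile just above it

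*SAP*

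**What the plan says.** SAP 1.1 gives HOMA-β as fasting insulin (µU/mL) × 360 divided by fasting glucose (mg/dL) minus 63, using insulin and glucose from the same day. The only exclusion is "Do not use the fasting blood glucose level of < 63 for calculation". Protocol 10.5.2 has the same formula with no exclusion.

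SAP 1.6, introduced with "Display digits are described as below", lists fasting glucose with digit 1 in mg/dL, that is, whole numbers. SAP 1.3 refers to Section 1.6 for the digits of the data being evaluated.

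SAP 6.3 covers the laboratory efficacy measures: "For fasting blood glucose level, fasting insulin level, fasting glucagon, HOMA-R, and HOMA"-β. For the changes it asks for summary statistics and a 95% CI of the mean, "calculated and the paired t-test will be performed", plus a bar graph. Summary statistics are defined in SAP 1.1 as "Number of patients, mean, standard deviation, minimum, first quartile, median, third quartile, and maximum". No transformation, rank test or outlier rule is given for HOMA-β.

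**The concern.** The guard and the denominator do not match. The formula fails at 63, but the rule removes only values below 63. A glucose of 63 is therefore kept by instruction and cannot be computed. The SAP does not say whether the programmer should treat it as missing. Software that returns infinity instead would leave the mean and SD of that table undefined.

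The second part is statistical. Close to 63 the denominator is only a few units, so the index is very large and changes steeply with glucose. A mean and a t-test on untransformed change can then be governed by one patient. At stake is the reading of HOMA-β change in any SAP 6.3 table that contains such a patient.

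**Working it through.** **No figure to reproduce.** The documents give no effect size, SD or power for HOMA-β, and Protocol 3.2 says that the 1,000 participants were not set on statistical grounds. The formula comes from SAP 1.1 and the two-sided 5% level from SAP 1.4. All patient values below are assumptions.

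**Step 1: the formula near the cut-off.** HOMA-β = 360 × insulin / (glucose − 63), at insulin 10 µU/mL:

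| Glucose (mg/dL) | 63 | 64 | 65 | 66 | 68 | 70 | 75 | 140 |
|---|---|---|---|---|---|---|---|---|
| HOMA-β | undefined (3,600/0) | 3,600 | 1,800 | 1,200 | 720 | 514 | 300 | 46.8 |

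One mg/dL moves the index by 1,800 between 64 and 65, but by about 0.6 between 140 and 141. HOMA-R (insulin × glucose / 405) has no such point: at 63 and 64 it is 1.56 and 1.58.

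**Step 2: one low reading after the start of treatment.** Assume 99 changes, normal in shape, with mean +9 and SD 30. Then t = 9 / (30/√99) = 2.98, p = 0.004; Wilcoxon p = 0.005; median 9.0.

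Add one patient with insulin 10 throughout, whose glucose goes from 140 to 64. The change is 3,600 − 46.8 = 3,553.2.

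- Mean: (99 × 9 + 3,553.2)/100 = 44.4.
- SD: √{[98 × 30² + 0.99 × (3,553.2 − 9)²]/99} = 355.7.
- t = 44.4/35.57 = 1.25, p = 0.21; 95% CI −26.1 to 115.0.

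The t-test p-value for other low readings, with insulin 10 at the 140 reading:

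| Low glucose | Insulin 10 at low reading | Insulin 5 | Insulin 3 |
|---|---|---|---|
| 64 | 0.21 | 0.14 | 0.07 |
| 65 | 0.14 | 0.054 | 0.017 |
| 66 | 0.087 | 0.022 | 0.006 |

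At insulin 10 the p-value is 0.034 at 68, 0.015 at 70 and 0.004 at 75. In every case the Wilcoxon p-value is about 0.003 and the median is 9.4.

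**Step 3: the low reading at baseline.** With 64 at baseline and 140 later (insulin 10), the change is −3,553.2 and the mean is (891 − 3,553.2)/100 = −26.6, with p = 0.46. The sign has reversed although the other 99 patients average +9. A baseline of 70 gives p = 0.45 and one of 75 gives p = 0.11. Wilcoxon p is about 0.009 and the median 8.6.

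**Step 4: more patients.** With 299 others of the same mean and SD (t = 9/(30/√299) = 5.19 before the addition), a post-treatment reading of 64 / 65 / 66 at insulin 10 gives p = 0.08 / 0.015 / 0.002.

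**Step 5: what each correction does.** Changing < 63 to ≤ 63 removes the undefined value but leaves 3,600 at 64, so it changes none of the p-values above. The rank test and median deal with the values just above 63.

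**The case against.** A reading of exactly 63 cannot be tabulated under any rule, so in practice it would probably drop out, and the corrected inequality then changes little. That is fair: the first part is mainly a correction of the text, so that the handling is stated and counted.

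The illustration is also a severe case. It holds insulin at 10 while glucose falls to 64, among only 99 other patients. With lower insulin, a reading further from 63 or a larger group, the effect shrinks, as the tables show. The documents give neither the frequency of readings near 63 nor the number of same-day insulin and glucose pairs. This limits the size of the claim. It does not remove the fragility, which is worse when the low reading is at baseline.

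The planned minimum, maximum, median and quartiles would let a reader see a value of 3,600. That stands too, and it is why the fix can build on existing output. But the only planned test, and the planned CI, still rest on the mean.

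A reader might infer that HOMA tests should be limited to patients without insulin. SAP 1.1 does define an insulin group ("Patients who will be treated with insulin preparation within 3 months prior to Nesina treatment and during Nesina treatment"), and SAP 6.3 tests it. But the zero denominator depends on glucose alone, so patients on secretagogues or SGLT-2 inhibitors can also read 63 or 64. Whether measured insulin includes injected insulin depends on assay properties that the documents do not give, and the shift may be nil. That restriction is not supported here as a remedy.

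**Conclusion.** The cut-off is wrong as written: SAP 1.1 keeps a glucose value at which its own formula has no result. The paired t-test and mean CI for HOMA-β change are a fragile choice for an index that rises so steeply just above 63. Under the assumed inputs, one patient reading 64 moves p from 0.004 to between 0.07 and 0.21, depending on insulin; at baseline (insulin 10) the same reading reverses the sign of the mean change.

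It would go too far to say that the survey's HOMA-β result will be decided by such a reading, because nothing in the documents shows that one will occur. The point is minor. HOMA-β is one of several supporting laboratory measures. The HbA1c analysis (SAP 6.1) and HOMA-R are unaffected.

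**What to change.** 1. SAP 1.1, HOMA-β: change the exclusion from < 63 to ≤ 63 mg/dL, and report the number of HOMA-β values excluded at each time point.
2. SAP 6.3, HOMA-β change only: add a Wilcoxon signed-rank test beside the paired t-test. State in advance that HOMA-β change is read from that test and from the median and quartiles already planned, and that the mean, its CI and the change graph are secondary.

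The cost is one character, one count per time point, one extra test and a change of emphasis on a supporting endpoint. The mean and its CI stay fragile, which is why they become secondary. No new data are needed, and the tabulation that Protocol 10.5.2 asks for is kept.
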